### **1.2.2. Clinical Studies**

Study AL002-1 assessed the safety, tolerability, PK, and pharmacodynamics (PD) of IV administration of AL002 administered as a single-dose to healthy volunteers as well as multiple doses to participants with mild to moderate AD. Study AL002-1 was closed to enrollment by Alector on 14 May 2020 given the available data already obtained and limitations on enrollment due to the coronavirus disease 2019 (COVID-19) pandemic.

AL002 was studied in 64 healthy volunteers enrolled in the first portion of the AL002-1 study, which evaluated single-dose IV infusion administration of AL002 with doses ranging from 0.003 to 60 mg/kg. All participants in these single-ascending dose cohorts reached the end of their dose-limiting adverse event (DLAE) assessment windows. Fifty-three participants were exposed to AL002, and 11 participants were on placebo. All participants have completed the study, with the exception of 1 participant (60 mg/kg), who withdrew consent after receiving one dose of AL002. The second portion of AL002-1 evaluated AL002 administered in multiple doses in participants with AD. Due to the closing of enrollment, only 5 of the planned 32 participants with AD were enrolled in the multiple dosing part. Three participants (2 on AL002 and 1 on placebo) were enrolled on a schedule that evaluated AL002 15 mg/kg weekly for 4 doses. Following a protocol amendment, an additional 2 participants (1 on AL002 and 1 on placebo) were enrolled on a schedule that evaluated AL002 60 mg/kg every 4 weeks for 2 doses. In this study, there were no deaths, no DLAEs, no treatment-related serious adverse events (SAEs), and no adverse events of special interest (AESIs). One participant in the pooled placebo group had a Grade 3 injury (attributed to trauma) that was serious and was considered unrelated to study drug. Two participants in the single-ascending dose part experienced adverse events (AEs) considered probably related to AL002 that led to withdrawal of study drug. Overall, AL002 was considered generally safe and well tolerated in this trial.

In the ongoing, randomized, double-blind, placebo-controlled, dose-ranging Phase 2 study, AL002-2, the AL002 is administered for up to 96 weeks via IV infusion every 4 weeks. To

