3.2 Participant Grouping

There are two treatment classes for the LTE and Integrated Analyses:

- **Group T-T** includes participants who were exposed to AL002 during the Core Study. They will continue at their Core Study AL002 dosage during the LTE Study if enrolled in the LTE Study. Group T-T is further broken down as AL002 15 mg/kg, 40 mg/kg, and 60 mg/kg treatment groups.

- **Group P-TC** includes participants who were exposed only to placebo during the Core Study. They will be assigned to the TC during the LTE Study if enrolled in the LTE Study. Group P-TC might be separated into placebo and TC treatment groups depending on the summaries/analyses.

For Group P-TC, the data collected when the participants were receiving placebo in the Core Study might be summarized and/or analyzed separately from the data collected once the participants received the first study drug administration in the LTE Study. The data collected when the participants were receiving placebo in the Core Study up to the day before the participants received the first study drug administration in the LTE Study (separately from the data collected in the LTE Study) is referred to as **the Placebo Data** throughout the SAP. And it includes the data from the placebo participants who did not enroll in the LTE Study. The data collected on or after the day when the participants received the first study drug administration in the LTE Study is referred to as **the TC Data** throughout the SAP.

The first dose date of AL002 refers to the earliest date of any amount of AL002 administered across the Core Study and the LTE Study. **The last dose date of AL002** refers to the latest date of any amount of AL002 administered across the Core Study and the LTE Study. **The first dose date of any study drug** refers to the earliest date of any study drug administered, including placebo, across the Core Study and the LTE Study.

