7.4.1.2.1 Integrated Descriptive Summaries of Safety Endpoints by Time Interval of Events Occurrence

Selected safety endpoints (as specified in Section 8) will be summarized by the categories of timing to occurrence of events since Core Study Day 1 (for Group T-T and placebo) or LTE Study Day 1 (for the Titration Cohort) in weeks: < 48 Weeks, $\geq 48 - < 96$ Weeks, $\geq 96 - < 144$ Weeks, and ≥ 144 Weeks. Timing to occurrence of events since Core Study Day 1 (for Group T-T and placebo) or LTE Study Day 1 (for the Titration Cohort) in weeks is calculated as the number of weeks between the Core/LTE Study Day 1 and event start date, i.e., timing to occurrence of events = (event start date - Core/LTE Study Day 1 + 1) / 7. In the event of missing or incomplete event start date, the same imputation rules as specified for the events apply.

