7.4.3 Adverse Events

AE related terms such as TEAE, SAE, and AESI are defined in Section 6.2.2.

An overall summary of AEs will present the number and percentage of participants who experienced at least 1 TEAE for the following events:

- TEAE (total and by maximum severity),
- Treatment-related TEAE (total and by maximum severity),
- TEAE leading to early study drug discontinuation,
- TEAE leading to study drug interruption,
- Treatment-emergent SAE,
- Treatment-related treatment-emergent SAE,
- Treatment-emergent AESI,
- Treatment-related treatment-emergent AESI,
- TEAE leading to death (i.e., outcome is fatal),

The number and percentage of participants who experienced at least 1 TEAE and the number and percentage of participants who experienced at least 1 treatment-related TEAE will be summarized by SOC, PT, and Severity. For other AEs described below, summaries will be provided by SOC and PT:

- TEAE (total and by severity),
- Treatment-related TEAE (total and by severity),
- TEAE leading to early study drug discontinuation,
- TEAE leading to study drug interruption,
- Treatment-emergent SAE,
- Treatment-related treatment-emergent SAE,

- Treatment-emergent AESI,
- Treatment-related treatment-emergent AESI,
- TEAE leading to death (i.e., outcome is fatal).

AEs will be summarized and listed first in alphabetic order of SOC and then by PT in descending order of total frequency within each SOC.

In addition to the above summary tables, TEAE, treatment-related TEAE, and treatment-emergent SAE will be summarized by PT only, in descending order of total frequency.

In addition to the by-participant data listing of all AEs, separate by-participant data listings will also be provided for the following:

- TEAE leading to early study drug discontinuation,
- Treatment-emergent SAE,
- Treatment-emergent AESI,
- TEAE leading to death.

For Integrated Analysis, all of the above summaries will be presented overall and also by the time intervals of event occurrence defined in Section 7.4.1.2.1. Denominators for percentages of events are determined by the numbers of participants at risk in each interval for each treatment group, which are those participants where $[\min(\text{last participation day, last dose date} + 90 \text{ days}) - \text{first dose date} + 1]/7$ is at least equal to the lower bound of the time interval.

For LTE Analysis, the following selected summaries will be provided for events during the LTE Study.

- Overall summary of AEs

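### The by-interval adverse event tables count everyone who reaches an interval's first day as fully at risk, so about 4 observed weeks on placebo and 8 in the Titration Cohort stand beside up to 48 on AL002

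*SAP*

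**What the plan says.** SAP 7.4.3 states that for the Integrated Analysis "all of the above summaries will be presented overall and also by the time intervals of event occurrence". The intervals are set in SAP 7.4.1.2.1: under 48 weeks, 48 to under 96, 96 to under 144, and 144 or more. Time runs from Core Study Day 1 for Group T-T and placebo, and from LTE Study Day 1 for the Titration Cohort.

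On denominators, SAP 7.4.3 says "Denominators for percentages of events are determined by the numbers of participants at risk in each interval for each treatment group". A participant qualifies when the week number reached by the earlier of last participation and last dose plus 90 days "is at least equal to the lower bound of the time interval". The rule does not use time observed inside the interval. SAP 7.4.2 summarises participant-years as exposure, but no adverse event rate uses them.

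Follow-up differs between groups by design:

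- SAP 3.2 takes Placebo Data only "up to the day before the participants received the first study drug administration in the LTE Study".
- SAP 3.1 puts that first LTE dose 4 weeks (±5 days) after the last Core dose.
- Protocol 1.2.2 describes the Core Study as one in which "the AL002 is administered for up to 96 weeks via IV infusion every 4 weeks".
- Protocol 3.2.4 places the last LTE visit 8 weeks after the last LTE dose.
- SAP 7.4.3.1 counts Group T-T events across both studies, and placebo and Titration Cohort events separately.

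**The concern.** A percentage of participants with an event depends on how long they are watched. If one column is watched for 4 weeks of an interval and another for 48, the percentages differ even when the underlying risk is the same.

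Long-term safety is a primary objective. The primary safety estimand in SAP Table 2-1 asks for AESI and SAE incidence by group over comparable lengths of time, and in these cells the interval rule does not provide that. The likely misreadings go in opposite directions: a late excess of events on AL002 over placebo, and an unusually low late rate after slow titration. The second also pulls down the AL002 total column, because SAP 7.1 pools the Titration Cohort into it.

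**Working it through.** **Schedule figures reproduced.** Last LTE dose at Day 337 and final visit at Day 393 (SAP visit windows): (393 − 337)/7 = 8.0 weeks, as Protocol 3.2.4 states. Week 96 at Core Day 673 and LTE entry at about Core Day 701: (701 − 673)/7 = 4.0 weeks, as SAP 3.1 states. Expected enrolment in SAP 3.5: 0.80 × 220 = 176 and 0.90 × 220 = 198.

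**Observed time in each interval.** With week = study day/7, Week 48 begins at Day 336, Week 96 at Day 672 and Week 144 at Day 1008. A full interval is 336 days.

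| Group and interval | Observed days | Weeks |
|---|---|---|
| Placebo roll-over, 96 to <144 | 672 to 700 = 29 | 4.1 (3.4 to 4.9 with ±5 days) |
| Non-roll-over, placebo or AL002, 96 to <144 | at most 672 to 763 = 92 (673 + 90 = 763) | at most 13.1 |
| Titration Cohort completer, 48 to <96 | 336 to 393 = 58 | 8.3 (7.6 to 9.0 with ±5 days) |
| AL002, 48 to <96 | 336 | 48.0 |
| AL002 completing Core and LTE, 96 to <144 | 336 | 48.0 |
| AL002, ≥144 | 1008 to 1093 = 86 | 12.3 |

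Each of these participants counts as one in the denominator. At the extreme, a Titration Cohort participant with a last dose on LTE Day 281 and an early termination visit on Day 337 enters the 48 to <96 row with 2 observed days.

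**Effect under equal risk.** Assume a constant hazard h = 0.12 per year in every group. The documents give no rate. The expected percentage is P(d) = 1 − exp(−h·d/365.25):

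- P(336) = 10.45%
- P(29) = 0.95%
- P(58) = 1.89%
- P(92) = 2.98%

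For the 96 to <144 row, let a fraction r of each group roll over (SAP 3.5 expects 80% to 90% of completers overall; the same r is assumed in both groups), and let non-roll-overs be observed for n days, from 29 to 92:

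- AL002 = r·P(336) + (1 − r)·P(n)
- Placebo = r·P(29) + (1 − r)·P(n)

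| r | n (days) | AL002 | Placebo | Ratio |
|---|---|---|---|---|
| 0.8 | 29 | 8.55% | 0.95% | 9.0 |
| 0.8 | 92 | 8.96% | 1.35% | 6.6 |
| 0.9 | 29 | 9.50% | 0.95% | 10.0 |
| 0.9 | 92 | 9.70% | 1.15% | 8.4 |

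The apparent excess is 6.6- to 10.0-fold. The same formulas give 6.8 to 10.3 at h = 0.05 and 5.8 to 8.6 at h = 0.5.

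For the 48 to <96 row, AL002 against Titration Cohort completers is 10.45/1.89 = 5.5. It is 5.7 at h = 0.05 and 4.8 at h = 0.5.

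**The case against.** Several points on the other side stand.

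- **The size has a ceiling.** A reader might infer an 11-fold artefact from 10.45% against 0.95%. That sets AL002 participants who all complete both studies against placebo participants who all roll over. Group T-T also includes non-roll-overs, who stop as early as the placebo ones.
- **Earlier LTE entry shrinks the late row.** Core dosing lasts up to 96 weeks, and the placebo windows in SAP 7.1.1.2 are cut at LTE Day 1 from Week 48 on. If participants entered 4 weeks after Core Week 48, 60 or 72, AL002 time in 96 to <144 would be about 12, 24 or 36 weeks. The mismatch would then move to 48 to <96, where placebo time would fall to about 4, 16 or 28 weeks.
- **Interim analyses are narrower.** SAP 8.1.3 limits the interim interval tables to four TEAE or SAE summaries, and the first interim has little LTE data. The full size applies to the final analysis.
- **The tables are descriptive.** No test is attached. The ARIA titration comparison in SAP 7.4.8 uses 48 weeks in both groups, and Kaplan-Meier curves are planned for ARIA.

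A reader might also infer that the 90-day allowance puts early placebo roll-overs in the 96 to <144 denominator with no placebo time there. The documents do not establish this. The rule takes the earlier of last participation and last dose plus 90 days, and SAP 7.4.3.1 counts placebo and Titration Cohort separately. If last participation is read within the Core Study, such a participant drops out. The inference holds only if that day runs into the LTE. SAP 6.1 does not settle which study is meant, so this is an ambiguity to close.

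Nor does the SAP claim that the intervals put groups on an equal time base. It says only that events "will be summarized by the categories of timing to occurrence of events since Core Study Day 1" (LTE Study Day 1 for the Titration Cohort). The percentages still sit side by side by group, and none of these points changes the denominator rule.

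**Conclusion.** The point holds. Applied as written, SAP 7.4.3 sets about 4 observed weeks for placebo roll-overs (at most about 13 for non-roll-overs) and about 8 for Titration Cohort completers beside up to 48 weeks on AL002. Under equal risk, the final-analysis 96 to <144 row would show about a 7- to 10-fold apparent AL002 excess over placebo, and the 48 to <96 row up to about a 5.5-fold apparent Titration Cohort deficit.

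These sizes assume a constant hazard of 0.12 per year in every group, full 96-week Core completion and, for the placebo comparison, 80% to 90% roll-over in both groups. They are smaller at an interim cutoff, and the late row shrinks with earlier LTE entry. The Core Study SAP, which defines placebo TEAEs, is not among the documents. The consequence is misleading descriptive safety tables, not a wrong test, so the change should be made but does not threaten the planned inference.

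**What to change.** In SAP 7.4.3:

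1. State that for the placebo column at-risk time, including the last participation day, ends the day before LTE Day 1.
2. Add an exposure-adjusted incidence rate to each interval row: participants with a first event in that interval, divided by person-time in it, with each participant's time stopped at that first event or at the end of observation. The stopping rule matters. Dividing by all observed time at an equal hazard of 0.5 per year gives 36.87%/(336/365.25) = 40 per 100 participant-years over a full interval, against 3.89%/(29/365.25) = 49 on placebo, a bias the other way.
3. Show observed person-time beside n.
4. Footnote the cells that planned follow-up does not span (placebo from Week 96, Titration Cohort from Week 48, AL002 arms from Week 144), saying that their percentages are not to be compared between groups. The counts can stay, so late events remain visible.

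The cost is a few sentences of SAP text and extra rate and person-time columns, from dates already collected.

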7.4.3.1 Adverse Events Counting Rules

For Group T-T, at the participant level, the following AE counting rules apply across two studies:

- A participant with more than one different AE in a particular SOC will be counted only once in the total of participants experiencing AEs in that particular SOC.
- A participant having experienced the same event, AE PT, more than once during the study will be counted only once in the number of participants with that event.
- If an event changes in intensity or in seriousness during the study, the participant will be counted only once with the worst grade and seriousness respectively.
- If the causal relationship to the study drug is assessed differently, it will be counted only once by considering the “worst” documented degree of relationship.

For Group P-TC, the same counting rules apply but per study/treatment, i.e., separately counted in Core Study (for placebo) and in LTE Study (for Titration Cohort).

AEs reported with a relationship to study drug of related will be counted as treatment related. If the relationship is missing on the electronic CRF, this event will be included as ‘related’, and this will be noted.

7.4.3.2 Deaths

If applicable, deaths will be summarized by SOC and PT, and will be listed including any appropriate information where available. All deaths observed in the study will be included in the summary and by-participant data listing.

7.4.4 Columbia Suicide Severity Rating Scale (C-SSRS)

For the C-SSRS, the number and percentage of participants with suicidal ideation, suicidal behavior, and non-suicidal self-injurious behavior as recorded on the C-SSRS scale, will be presented for each visit (refer to [Table 7-1](#) and [Table 7-2](#) for analysis visit window definitions), and overall during the treatment period.

When summarizing the lifetime history of suicidal ideation, suicidal behavior, suicidal ideation or suicidal behavior, and non-suicidal self-injurious behavior, all related data recorded on the Screening/Baseline version will be included regardless of whether the assessment date is prior to, on, or after Core Study Day 1.

When summarizing the baseline (past 6 months for suicidal ideation, or past 2 years for suicidal behavior and non-suicidal self-injurious behavior), only related data recorded on the Screening/Baseline version prior to or on Core Study Day 1 will be included.

Only data recorded on the Since Last Visit version after Core Study Day 1 will be included in the treatment period.

A shift table from Core baseline (past 6 months for suicidal ideation, or past 2 years for suicidal behavior) to each post-baseline visit and to overall during the treatment period will be provided for suicidal ideation, suicidal behavior, and no suicidal ideation or suicidal behavior. For overall, the response with the most severe suicidal ideation and suicidal behavior will be selected for a participant.

All C-SSRS data will be listed.

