### 6.3.11. Columbia-Suicide Severity Rating Scale

Suicidality will be assessed regularly throughout the study through participant completion of the C-SSRS (Table 9). The C-SSRS is an interview-based instrument used to assess incidence of suicidal ideation and behavior. Assessments will assess suicidal ideation and behavior since the previous visit. The C-SSRS is administered to the participant and measures 5 subtypes of suicidal ideation and behavior considered by health authorities to be important to capture in a prospective assessment of suicidality (FDA 2012).

Any change in the C-SSRS score indicating the presence of suicidality should be immediately evaluated by the Investigator and reported to the Medical Monitor. Participants who are suicidal based on the C-SSRS will be referred for appropriate psychiatric evaluation and management per local clinical practice. When the psychiatric evaluation verifies suicidal ideation or behavior, this must be recorded as an AE.

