6.2.3 Columbia-Suicide Severity Rating Scale (C-SSRS)

Two versions of the C-SSRS were used in the Core Study: a Screening/Baseline version and a Since Last Visit version. The Screening/Baseline version of the C-SSRS assesses the lifetime suicidal ideation and behavior and non-suicidal self-injurious behavior, the suicidal ideation in the past 6 months and suicidal behavior and non-suicidal self-injurious behavior in the past 2 years. The Screening/Baseline version of the C-SSRS was administered on Core Study Day 1 prior to dosing. The Since Last Visit version of the C-SSRS assesses suicidal thoughts or behaviors the participant may have had since the last time the C-SSRS was administered as specified in the Schedules of Assessments in the protocol.

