7.1.1.2 Analysis Visit Window Definitions

In LTE and Integrated Analyses, analysis visit windows based on Core Study Day and LTE Study Day will both be implemented.

7.1.1.2.1 *Safety and Pharmacokinetic Data*

Unless otherwise specified, for safety and PK data, the upper bound of a post-baseline analysis visit (except for “>90 Days Post Last Dose”) is the earlier date of specified upper limit and the last dose date of study drug plus 90 days. All safety and PK data that were collected beyond the last dose date of study drug plus 90 days will be assigned the analysis visit window “>90 Days Post Last Dose”.

Safety and PK data will be summarized based on the analysis visits excluding “>90 Days Post Last Dose” (hereinafter may be referred to as “visit”), when applicable. Safety and PK data with “>90 Days Post Last Dose” analysis visit window will only be listed.

Safety and PK data will be allocated to analysis visits corresponding to the analysis visit window intervals in which they fall in as specified in [Error! Not a valid bookmark self-reference.](#) to [Table 7-25.](#)

For safety data, the analysis visits will be displayed in the format of “Week x”. For Group T-T, “Week x” refers to the analysis visits based on Core Study Day. For the Placebo Data of Group P-TC, as defined in Section 3.2, “Week x” refers to the analysis visits based on Core Study Day; and for the TC Data as defined in Section 3.2, “LTE Week x” based on LTE Study Day will be abbreviated and displayed as “Week x”.

Table 7-1. Analysis Visit Windows for C-SSRS Assessments Based on Core Study Day^a

| Analysis Visit | Target Day | T-T Analysis Visit Window | Placebo Analysis Visit Window ^b |
|----------------|------------|---------------------------|--|
| Core Baseline | 1 | ≤ 1 | ≤ 1 |
| Week 24 | 169 | [2, 253] | [2, 253] |
| Week 48 | 337 | [254, 421] | [254, min (421, LTE Day 1)] |
| Week 72 | 505 | [422, 533] | [422, min (533, LTE Day 1)] |
| Week 80 | 561 | [534, 617] | [534, min (617, LTE Day 1)] |
| Week 96 | 673 | [618, 687] | [618, min (687, LTE Day 1)] |
| Week 100 | 701 | [688,715] | [688, LTE Day 1] |
| Week 104 | 729 | [716, 743] | |
| Week 108 | 757 | [744, 771] | |
| Week 112 | 785 | [772, 799] | |
| Week 116 | 813 | [800, 827] | |
| Week 120 | 841 | [828, 855] | |
| Week 124 | 869 | [856, 883] | |
| Week 128 | 897 | [884, 911] | |

| Analysis Visit | Target Day | T-T Analysis Visit Window | Placebo Analysis Visit Window ^b |

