|----------------|------------|---------------------------|--|
| Week 132 | 925 | [912, 939] | |
| Week 136 | 953 | [940, 967] | |
| Week 140 | 981 | [968, 995] | |
| Week 144 | 1009 | [996, 1023] | |
| Week 148 | 1037 | [1024, 1065] | |
| Week 156 | 1093 | > 1065 | |

^a Target Day and Core Study Day are based on Core Study Day 1.

^b LTE Day 1 represents Core Study Day of date of LTE Study Day 1. If no such date, use Core study day of the last visit date among Core visits and LTE screening visit.

Table 7-2. Analysis Visit Windows for C-SSRS Assessments Based on LTE Study Day^a

| Analysis Visit | Target Day | Analysis Visit Window |
|----------------|------------|-----------------------|
| LTE Baseline | 1 | ≤ 1 |
| LTE Week 4 | 29 | [2, 43] |
| LTE Week 8 | 57 | [43, 71] |
| LTE Week 12 | 85 | [72, 99] |
| LTE Week 16 | 113 | [100, 127] |
| LTE Week 20 | 141 | [128, 155] |
| LTE Week 24 | 169 | [156, 183] |
| LTE Week 28 | 197 | [184, 211] |
| LTE Week 32 | 225 | [212, 239] |
| LTE Week 36 | 253 | [240, 267] |
| LTE Week 40 | 281 | [268, 295] |
| LTE Week 44 | 309 | [296, 323] |
| LTE Week 48 | 337 | [324, 365] |
| LTE Week 56 | 393 | > 365 |

^a Target Day and LTE Study Day are based on LTE Study Day 1, unless indicated otherwise.

Table 7-3. Analysis Visit Windows for Hematology, Chemistry and Urinalysis Assessments Based on Core Study Day^a

| Analysis Visit | | Target Day | T-T Analysis Visit Window | Placebo Analysis Visit Window ^b |
|--|--------------------------|------------|---------------------------|--|
| Core Baseline | | - | ≤ 1 | ≤ 1 |
| Week 2 | | 15 | [2, 22] | [2, 22] |
| Week 4 | | 29 | [23, 36] | [23, 36] |
| Week 6 | | 43 | [37, 64] | [37, 64] |
| Week 12 (Hematology and Chemistry only) | | 85 | [65, 141] | [65, 141] |
| Week 28 | Hematology and Chemistry | 197 | [142, 239] | [142, 239] |
| | Urinalysis | | [65, 323] | [65, 323] |
| Week 40 (Hematology and Chemistry only) | | 281 | [240, 323] | [240, min (323, LTE Day 1)] |
| Week 52 | | 365 | [324, 463] | [324, min (463, LTE Day 1)] |
| Week 80 | | 561 | [464, 617] | [464, min (617, LTE Day 1)] |
| Week 96 | | 673 | [618, 687] | [618, min (687, LTE Day 1)] |
| Week 100 | | 701 | [688, 743] | [688, LTE Day 1] |
| Week 112 (Hematology and Chemistry only) | | 785 | [744, 841] | |
| Week 128 | Hematology and Chemistry | 897 | [842, 939] | |
| | Urinalysis | | [744, 1037] | |
| Week 140 (Hematology and Chemistry only) | | 981 | [940, 1037] | |
| Week 156 | | 1093 | > 1037 | |

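### The C-SSRS rows labelled Week 24 and Week 48 cover 24 weeks for placebo and Group T-T but 4 weeks for the Titration Cohort, and the SAP makes no allowance for it

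*SAP*

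**What the plan says.** C-SSRS is a primary safety endpoint (Protocol Table 1; SAP Table 2-1, Part 2). Five provisions of the SAP together determine its table.

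- **The form.** According to SAP 6.2.3, the on-treatment form "assesses suicidal thoughts or behaviors the participant may have had since the last time the C-SSRS was administered". Section 7.4.4 restricts on-treatment data to it: "Only data recorded on the Since Last Visit version after Core Study Day 1 will be included in the treatment period".
- **Core visits.** Table 7-1 starts with "Week 24 | 169 | [2, 253] | [2, 253"] and "Week 48 | 337 | [254, 421] | [254, min (421, LTE Day 1")], then Weeks 72, 80, 96 and 100. The columns are analysis visit, target day, Group T-T window and placebo window.
- **LTE visits, Titration Cohort.** Table 7-2 has a row every 4 weeks to LTE Week 48, for example "LTE Week 24 | 169 | [156, 183"], and then LTE Week 56.
- **Labels and columns.** Section 7.1.1.2.1 drops the LTE prefix for the Titration Cohort when safety data are displayed. Section 7.4.1.2 puts placebo, the AL002 dose groups and the Titration Cohort side by side in the integrated summary.
- **Summaries.** Section 7.4.4 states what it tabulates: "For the C-SSRS, the number and percentage of participants with suicidal ideation, suicidal behavior, and non-suicidal self-injurious behavior as recorded on the C-SSRS scale". It gives these per visit and overall, and adds a shift table from Core baseline (past 6 months for ideation, past 2 years for behavior) to each visit and to overall. The overall entry takes each participant's worst response. Nothing is said about unequal recall periods.

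The LTE protocol words the recall period differently. Protocol 6.3.11: "Assessments will assess suicidal ideation and behavior since the previous visit".

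**The concern.** A percentage from a form that asks about the time since the last form depends on how long that time was. Under one row label, two columns would report different lengths of experience. At equal underlying risk, a 4-week form picks up no more than a 24-week form, and usually less. Someone scanning the Week 24 row could take a lower Titration Cohort figure as reassurance. Someone following Group T-T down the table could take a drop after roll-over as improvement with time on drug.

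The shift table has the same problem. The ideation baseline covers 6 months, which roughly matches a 24-week row but not a 4-week row.

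**Working it through.** **Step 1. Reproduce the visit grid.** Target day = 7 × week + 1. Week 24 gives 169, Week 48 gives 337, Week 96 gives 673 and LTE Week 56 gives 393. All 19 post-baseline rows of Table 7-1 and all 13 of Table 7-2 agree.

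The Core cut points are midpoints of adjacent target days: (169 + 337)/2 = 253, (337 + 505)/2 = 421, (505 + 561)/2 = 533, (561 + 673)/2 = 617 and (673 + 701)/2 = 687. The windows therefore leave no sign of another planned Core form between the listed weeks.

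**Step 2. Look-back = difference between adjacent target days ÷ 7.**

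| Column | Row | Look-back (weeks) |
|---|---|---|
| Placebo, Group T-T | Weeks 24, 48, 72 | 24 each |
| Placebo, Group T-T | Week 80 | 8 |
| Placebo, Group T-T | Week 96 | 16 |
| Placebo, Group T-T | Week 100 | 4 |
| Group T-T | Weeks 104 to 148 | 4 each |
| Group T-T | Week 156 | 8 |
| Titration Cohort | LTE Weeks 4 to 48 | 4 each |
| Titration Cohort | LTE Week 56 | 8 |

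Placebo and the Titration Cohort share only the labels Week 24 and Week 48. At both, the ratio is 24/4 = 6. For Group T-T the step at roll-over is 16/4 = 4.

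**Step 3. From look-back to percentages.** The documents give no suicidality rate, so every value here is an assumption. Let p be the chance of a positive 4-week form. With independent, fully recalled episodes at constant risk, the chance of a positive k-week form is 1 − (1 − p)^(k/4).

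| p | 24-week form | Ratio to 4-week form |
|---|---|---|
| 0.1% | 0.60% | 5.99 |
| 1% | 5.85% | 5.85 |
| 5% | 26.49% | 5.30 |
| 10% | 46.86% | 4.69 |

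At p = 1% a 16-week form gives 3.94%, so the roll-over step is 3.94-fold.

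Now let a share s of the 4-week positives come from people who are positive on every form. With c = s·p and q = (p − c)/(1 − c), the 24-week chance is c + (1 − c)[1 − (1 − q)^6]. At p = 1%:

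| s | 24-week form | Ratio |
|---|---|---|
| 0% | 5.85% | 5.85 |
| 25% | 4.67% | 4.67 |
| 50% | 3.46% | 3.46 |
| 75% | 2.24% | 2.24 |
| 100% | 1.00% | 1.00 |

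**Step 4. The overall row.** Placebo contributes about 96 to 100 weeks and 5 or 6 forms. The Titration Cohort contributes about 48 to 56 weeks and 12 or 13 forms. Longer follow-up raises the placebo figure: at p = 1% with independent episodes, (1 − 0.99^24)/(1 − 0.99^12) = 21.4%/11.4%, or about 1.89. More frequent questioning raises the Titration Cohort figure if recall is incomplete. The documents do not allow the two to be netted.

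**The case against.** **A reader might infer that reported suicidality must fall six-fold.** The documents do not support that. Six is the ratio of look-backs at two labels. The ratio of percentages comes near six only for rare, independent, fully recalled episodes, and tends to 1 as ideation becomes persistent. For Group T-T the change at roll-over is four-fold in look-back.

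**A reader might also infer that the overall row is biased against the Titration Cohort**, because it has 12 interviews in 48 weeks against 2 for placebo. Those counts are right for the first 48 weeks, but the planned overall row runs over the whole treatment period, in which placebo has about twice the follow-up. The two arguments also pull against each other. The six-fold figure needs full recall over 24 weeks, whereas the interview-count argument needs recall to fail.

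**No C-SSRS comparison is planned.** Section 7.4.4 is descriptive, the two hypotheses in SAP 3.4 concern CDR-SB and ARIA, and all C-SSRS data are listed. This limits the harm. It does not make rows with the same label comparable.

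**A common-interval view partly exists.** Suicidality verified by psychiatric evaluation must be recorded as an AE (Protocol 6.3.11), and SAP 7.4.1.2.1 and 7.4.3 summarize AEs over common intervals with at-risk denominators. That covers verified cases only, not C-SSRS responses.

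**Core frequency is inferred.** The C-SSRS row of the protocol's schedule is redacted and the Core protocol was not supplied. The windows used here are nevertheless the ones that build the table.

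**The recall wording may differ.** If Core raters looked back only to the previous 4-weekly dosing visit, the per-visit gap would largely close. Two Core forms would then cover about 2 × 4 = 8 of the first 48 weeks, against all 48 for the Titration Cohort, and the cumulative comparison would break instead. SAP 6.2.3 describes the Core form and points to the longer look-back; the differing sentence stands in the LTE protocol.

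**Conclusion.** The concern holds for comparability. As written, the integrated C-SSRS table sets a 24-week look-back beside a 4-week one at Weeks 24 and 48. It also follows Group T-T through look-backs of 24, 24, 24, 8, 16 and then 4 weeks with nothing to warn the reader. Per-visit percentages and shifts should not be compared between placebo and the Titration Cohort, or across the Core-to-LTE change. The overall row should not be compared between placebo and the Titration Cohort.

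The look-back ratios (six-fold and four-fold) follow from the SAP's target days and the recall wording of 6.2.3. The effect on percentages is not fixed by the plan. In the cases worked above it ranges from none to nearly six-fold, depending on the assumed rate and persistence. The plan therefore does not guarantee that titrated AL002 will look safer than placebo, and the direction of the overall row is unknown. This is a reporting weakness in a primary safety endpoint that is cheap to repair before the final tables.

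**What to change.** In SAP 7.4.4:

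1. Keep the per-visit rows, which preserve the 4-week detail during titration, and footnote the look-back for each column.
2. Add rows for any positive response (the worst, where severity is shown) over common 24-week blocks, counted from Core Day 1 for Group T-T and placebo and from LTE Day 1 for the Titration Cohort. Use at-risk denominators of the kind in 7.4.3, and show the number of forms per participant. Build the same blocks into the shift table. The Week 80 and Week 96 forms together fill the fourth block (8 + 16 = 24 weeks).
3. State where the Week 100 form goes. For Group T-T it falls in the block after Week 96; for placebo it is a 4-week remainder. Label the interval that ends at Week 156 (LTE Week 56 for the Titration Cohort) as a short block.
4. Compare placebo with the Titration Cohort over the common first 48 weeks, not through the overall row. Say that interview frequency still differs (2 forms against 12).
5. Reconcile the recall period in Protocol 6.3.11 with SAP 6.2.3, and record which one Core raters used.

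The cost is SAP wording and extra table rows; no new data are needed. Pooling does not remove bias from more frequent questioning, so that has to be stated with the results.
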